7.14 Changes in the Statistical Analysis Plan

Summary of Changes from Version 2 to Version 3 of the SAP		
Location	Description	Rationale
Throughout protocol	TAK-573 was changed to modakafusp alfa.	To align with the protocol.
Title	“Relapsed” was added.	To align with the protocol.
Section 4.3 Section 4.4 Section 5.3 Section 6.0 Section 7.9.2 Section 7.10 Section 7.13	Part 3 extension study design, objectives, endpoints, sample size and analysis approaches were added to this study	To align with the protocol
Section 4.1 Section 4.4 Section 5.1	Part 1 escalation exploratory objectives and endpoints were clarified	To align with the protocol
Section 4.2 Section 4.4 Section 5.2	Part 2 expansion secondary objectives and endpoints were clarified Part 2 expansion exploratory objectives and endpoints were clarified	To align with the protocol
Section 5 Section 7.9	Clarified the definition of duration of response	To align with the protocol
Section 7.14	Extended loss-to-follow-up rule for PFS and TTP analysis was added	To provide details in the derivation algorithm

Section 7.4	The definition of refractory was updated	To align with the definition in the protocol
Section 7.9	Best unconfirmed response analysis was removed; The algorithm of response confirmation was updated	To provide details in the derivation algorithm
Section 7.11.3	Additional ADA analyses were added under immunogenicity analysis	To include additional ADA analyses for assessment
Section 7.9.1	The analysis approach for time to response was changed from time-to-event analysis to descriptive analysis	To evaluate the endpoint in an appropriate approach
Appendix A	The listing of DLT-like events was added	To include for evaluation of DLT-like events
Appendix C	The algorithms of DLT-like events were added	To provide details in the derivation algorithm

Summary of Changes from Version 1 to Version 2 of the SAP		
Location	Description	Rationale
Section 6	Changed planned sample size for phase 2	To align sample size with change in study endpoints.
Section 7.2	Added response-evaluable analysis set	To align statistical content with change in study endpoints.
Section 7.4	Added the description of the measurable disease at baseline	To clarify the algorithm to define patients with measurable disease at baseline
Section 7.8	Added clinical benefit rate and disease control rate as a secondary endpoint for phase 1 and as a primary endpoint for phase 2	To adjust endpoints to be more relevant in this early-phase study.
Section 7.8	Removed overall survival as a secondary endpoint	To align with the protocol and reflect determination that the endpoint of overall survival is not informative without a comparator group.
Section 7.8	Added the definition of confirmed response and the scenarios to claim a confirmed response	To clarify the algorithm of confirmed responses.

Section 7.11	Added description of analysis of AESI	To align with the protocol and monitor the AESI.
Section 7.11	Added oxygen saturation as a vital sign	To align with the protocol.
Section 7.12	Added criteria for early termination	To clarify conditions for early termination and clarify that no interim analysis is planned.
Appendix B	Added imputation rules for partial dates	To clarify the imputation rules for different types of partial dates.

Appendix A By-Subject Listings:

In addition to the analysis outputs outlined above in the main text, separate by-patient listings will also be generated to include the following information. This includes but is not limited to:

- Disposition (date of first dose, date of last dose, number of cycles, reason for discontinuation of study treatment).
- Populations.
- Significant protocol deviations.
- Demographics.
- Study drug exposure.
- TEAEs.
- TEAEs leading to study drug discontinuation.
- Serious AEs.
- All deaths.
- DLTs during Cycle 1 in dose escalation.
- Pharmacokinetic concentrations.
- ADA.
- Efficacy (response assessments, All time to events).

Appendix B Date Imputation Rules

Incomplete Dates in the Screening Period

1. If only the day-component is missing, the first day of the month will be used if the year and the month are the same as those for the first dose of study drug. Otherwise, the fifteenth will be used.
2. If only the year is present, and it is the same as the year of the first dose of study drug, the fifteenth of January will be used unless it is later than the first dose, in which case the date of the first of January will be used.
3. If only the year is present, and it is not the same as the year of the first dose of study drug, the fifteenth of June will be used.

Incomplete Adverse Event Onset Date

Assumption: For on-study Adverse Events.

If *year* is missing (or completely missing): set to the date of first dose.

If (*year* is present and *month* and *day* are missing) or (*year* and *day* are present and *month* is missing):

If *year* = year of first dose: set the date to the first dose date.

If *year* < year of first dose: set *month* and *day* to December 31st.

If *year* > year of first dose: set *month* and *day* to January 1st.

If *month* and *year* are present and *day* is missing:

If *year* = year of first dose, and:

If *month* = month of first dose: set *day* to day of first dose.

If *month* < month of first dose: set *day* to last day of *month*.

If *month* > month of first dose: set *day* to 1st day of *month*.

If *year* < year of first dose: set *day* to last day of month.

If *year* > year of first dose: set *day* to 1st day of month.

For all other cases: set to date of first dose.

Incomplete Adverse Event Resolution Date

Assumption: For on-study Adverse Events.

If *day* is missing but *month* and *year* are non-missing, impute as the earliest of:

- Last day of the *month*
- Data cutoff date
- Death date

If *day* and *month* are missing, impute as the earliest of:

- December 31st
- Data cutoff date
- Death date

If date is completely missing (i.e. AE is ongoing), impute as earliest of:

- Data cutoff date

- Treatment discontinuation date (i.e. last dose date) + 30 days
- Death date

Incomplete Concomitant Medication Start Date/Prior Therapy Start Date/Progression Date during Prior Therapy

If *year* is missing (or completely missing): do not impute.

If (*year* is present and *month* and *day* are missing) or (*year* and *day* are present and *month* is missing):

Set *month* and *day* to January 1st.

If *year* and *month* are present and *day* is missing:

Set *day* to 1st day of month.

Incomplete Concomitant Medication End Date

If *year* is missing (or completely missing): do not impute.

If (*year* is present and *month* and *day* are missing) or (*year* and *day* are present and *month* is missing):

Set *month* and *day* to December 31st.

If *year* and *month* are present and *day* is missing:

Set *day* to last day of the month.

Incomplete Subsequent Anti-Cancer Therapy Start Date

If *year* is missing (or completely missing): set to date of last dose of study treatment + 1

If (*year* is present and *month* and *day* are missing) or (*year* and *day* are present and *month* is missing):

If *year* > *year* of the last dose: Set *month* and *day* to January 1st.

If *year* = *year* of the last dose: Set *month* and *day* to date of last dose of study treatment +1.

If *year* and *month* are present and *day* is missing:

Set *day* to 1st day of month if the resulting imputed date is greater than date of last dose.

Otherwise set the imputed date to date of last dose + 1.

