The maximum percent reduction will be plotted in the following hierarchical order:

- [1] Plot the worse (higher) value of the maximum percent reduction from baseline in serum and urine M-protein if the patient has both serum and urine M-protein measurable;
- [2] Plot Serum M-protein maximum percent reduction from baseline if data is available;
- [3] If [2] is not feasible, plot Urine M-protein maximum percent reduction from baseline if data is available;
- [4] If both [2] and [3] are not feasible, plot maximum percent reduction from baseline for difference between two types of Serum FLC if data is available.

Difference between two types of serum free light chain (FLC)

The percent change from baseline for difference between two types of serum FLC is defined as:

$$(\text{post-baseline difference} - \text{baseline difference}) / \text{baseline difference} * 100\%$$

To calculate the difference, the “involved” and “non-involved” light chains must be determined at first based on the ratio of non-missing values for Serum Kappa LC protein and Serum Lambda LC protein at baseline.

The detailed algorithm is provided as below:

- If the baseline ratio of (Kappa LC/Lambda LC) > 1.65 , then Kappa LC is defined as involved FLC, and Lambda LC is defined as non-involved FLC. Then:
Difference between involved and uninvolved = Kappa LC-Lambda LC
- If the baseline ratio of (Kappa LC/Lambda LC) < 0.26 , then Lambda LC is defined as involved FLC, and Kappa LC is defined as non-involved FLC:
Difference between involved and uninvolved = Lambda LC-Kappa LC
- If the baseline ratio of (Kappa LC/Lambda LC) ≤ 1.65 and ≥ 0.26 , then “involved” and “non-involved” FLC cannot be determined (ratio is normal), and maximum percent reduction from baseline for difference between two types of Serum FLC won’t be available.

7.8.2.2 *Secondary Efficacy Analysis*

ORR based on Investigator Assessment

ORR based on investigator-assessed response will be analyzed as one of the secondary endpoints. It will be analyzed based on the confirmed responses by using the same analysis approach as for IRC-assessed ORR.

DOOR

DOOR is defined as the time from first documented evidence of confirmed PR or better until the earliest date of a confirmed PD per IMWG, or death among patients who achieve a response (i.e., confirmed PR or better). Responders without confirmed PD or death will be censored at the censoring time point for PFS as specified in Table 1.

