Duration of disease control is defined as the time from first documented evidence of SD or better until the earliest date of a confirmed PD per IMWG, or death among patients who achieve a SD or better. Patients without confirmed PD or death will be censored at the censoring time point for PFS as specified in Table 1.

Duration of disease control will be analyzed at the time of primary ORR analysis, also at final analysis (study close out), based on responses assessed by both IRC and investigator.

Duration of disease control will be summarized using the Kaplan-Meier method by dose level for patients with a SD or confirmed MR or better. Median duration of disease control, first and third quartiles and 95% CI, will be estimated using the Brookmeyer-Crowley method.

PFS

PFS is defined as the time from the date of first dose until the earliest date of confirmed PD per IMWG, or death due to any cause. PFS will be analyzed at the time of primary analysis of ORR, also at final analysis (study close out), based on responses assessed by both IRC and investigator.

A summary of the assignments for progression and censoring dates for PFS are specified in Table 1 below.

Table 1 Assignments for Progression and Censoring Date for PFS Analysis

Scenarios	Event date/censoring date	Event status
No (or inadequate) baseline tumor assessments ¹	Date of the first dose	Censored
No post-baseline assessments	Date of the first dose	Censored
Confirmed progression documented without extended loss-to-follow-up time (two or more missed cycles) ⁴	Date of assessment of the earliest date of the confirmed progression	Event
No confirmed progression or death	Date of last adequate assessment of response ²	Censored
Subsequent anti-cancer therapy started (before documented confirmed progression or death) ³	Date of last adequate assessment of response ² (prior to the initiation of the subsequent anti-cancer therapy)	Censored
Death without extended loss-to-follow-up time	Death date	Event
Death or progression after an extended loss-to-follow-up time (two or more missed cycles) ⁴	Date of last adequate assessment of response ² (prior to missed assessments)	Censored

1. Adequate baseline assessment is defined as at baseline, a patient has at least one of the following measurements:
 - a. Serum M-protein $\geq 0.5\text{g/dL}$ ($\geq 500\text{ mg/dL}$) or
 - b. Urine M-protein $\geq 200\text{ mg/24 hours}$ or

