 - c. Serum FLC assay: Involved FLC level $\geq 10\text{ mg/dL}$ ($\geq 100\text{ mg/L}$) and an abnormal serum FLC ratio (<0.26 or >1.65)
2. An adequate assessment is defined as an assessment where the IRC/investigator determined response is sCR, CR, VGPR, PR, MR, or SD prior to a subsequent anti-cancer therapy. An unconfirmed PD assessment is also considered as an adequate assessment.
3. If PD or death and the subsequent anti-cancer therapy occur on the same day, it is assumed that the progression or death was documented first (e.g., event status is an event, and the date of event is the date of progression or death). If the subsequent anti-cancer therapy is initiated prior to any adequate assessment, censoring date should be the date of the first dose.
4. Refer to Section 7.1.4 “Extended Loss-to-follow-up”

PFS will be summarized using the Kaplan-Meier method by dose level. Median PFS, first and third quartiles, 3-month, 6-month, 9-month, 12-month PFS rate (or later time points if data

permits), and 95% CIs will be estimated using the Brookmeyer-Crowley method. A Kaplan-Meier plot of PFS time will also be provided.

TTP

TTP is defined as the time from the date of the first dose until the earliest date of confirmed PD per IMWG.

TTP will be analyzed at the time of primary analysis of ORR, also at final analysis (study close out), based on responses assessed by both IRC and investigator.

A summary of the assignments for progression and censoring dates for TTP are specified in Table 2.

Table 2 Assignments for Progression and Censoring Date for TTP Analysis

Scenarios	Event date/censoring date	Event status
No (or inadequate) baseline tumor assessments ¹	Date of the first dose	Censored
No post-baseline assessments	Date of the first dose	Censored
Confirmed progression documented without extended loss-to-follow-up time (two or more missed cycles) ⁴	Date of assessment of the earliest date of the confirmed progression	Event
No confirmed progression or death	Date of last adequate assessment of response ²	Censored
Subsequent anti-cancer therapy started (before documented confirmed progression) ³	Date of last adequate assessment of response ² (on or prior to the initiation of the subsequent anti-cancer therapy)	Censored
Death	Date of last adequate assessment of response ² prior to death	Censored

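### A subsequent-therapy date with a missing day is imputed without reference to PD, so a first PD after the last dose and later in the same month can become censoring in PFS, TTP and DOR

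*SAP*

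**What the plan says.** SAP Appendix B, under incomplete subsequent anti-cancer therapy start dates, covers the case of known year and month. The missing day becomes the "1st day of month if the resulting imputed date is greater than date of last dose". The next line reads "Otherwise set the imputed date to date of last dose + 1". The PD date appears nowhere in the rule.

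SAP Section 7.8.2.2 then uses the order of the two dates:

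- **PFS, Table 1.** The row "Subsequent anti-cancer therapy started (before documented confirmed progression or death") is censored, at the last adequate assessment "prior to the initiation of the subsequent anti-cancer therapy".
- **TTP, Table 2.** The corresponding row is "Subsequent anti-cancer therapy started (before documented confirmed progression"), also censored.
- **DOR.** "Responders without confirmed PD or death will be censored at the censoring time point for PFS as specified in Table 1". The durations of clinical benefit and disease control use the same censoring point.
- **Ties, Table 1 note 3.** When both dates coincide, the note takes PD or death to have come before the new therapy. Table 2 has a matching note for PD.

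The confirmation rules in SAP Section 7.8.1 also depend on the therapy date. A single PD counts as confirmed if it is the last assessment before subsequent therapy, or the last before treatment is stopped because of PD.

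**The concern.** The imputation takes the earliest admissible day, whatever is known about progression. A patient can progress at a study visit, move to new therapy later that month, and have the new therapy recorded by month only. The imputed start can then precede the PD. The sequence is reversed in the analysis, and a PD event is replaced by censoring at an earlier assessment.

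The patients exposed to this are those who progressed and then changed treatment. The censoring is therefore informative and would tend to lengthen the Kaplan-Meier estimates of PFS, TTP and DOR.

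**Working it through.** The plan states no figure for this point, so there is none to reproduce. The check codes the rule and follows it through.

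**Inputs.** Let L be the last dose date, P the earliest date of the PD, and F the 1st of the recorded month.

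- Imputed therapy date T (Appendix B): T = F if F > L, otherwise T = L + 1 day.
- Status (Table 1 and note 3): event if P ≤ T, censored if P > T.

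**Step 1: where nothing goes wrong.** Both branches give T > L. If P ≤ L, then P < T and the event stands. A PD dated on or before the last dose is always safe.

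**Step 2: where it goes wrong.** The status changes when all of these hold: P > L, P lies in the recorded month, the true therapy start is on or after P, and P > T.

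**Step 3: example with a 28-day gap (assumed dates).** Last dose 20 March, PD 17 April, true new therapy 25 April, recorded only as April.

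- True dates: 17 April ≤ 25 April, so a PFS event on 17 April.
- SAP rule: F = 1 April > 20 March, so T = 1 April. Since 17 April > 1 April, the patient is censored at the last adequate assessment before 1 April. If that was the 20 March dosing visit, follow-up ends 28 days before the PD.

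**Step 4: how much of the date space is affected.** Take every P in 2023 with every true therapy start in the same month on or after P. A month of n days has n(n + 1)/2 such pairs:

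- 31 days: 496 × 7 months = 3,472
- 30 days: 465 × 4 months = 1,860
- 28 days: 406 × 1 month = 406
- Total: 5,738

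Only P on the 1st is kept as an event, by the same-day rule. That accounts for n pairs per month, or 365 in the year. The remainder is 5,738 − 365 = 5,373, and 5,373/5,738 = 93.6%. In a 30-day month it is 435/465 = 93.5%.

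The documents do not give the gap from last dose to PD, so gaps of 14, 28, 35 and 42 days were assumed. The count was 5,373 at each. The last-dose-plus-1 branch behaves the same way: 1,720 of 1,720 such pairs are censored at a 14-day gap, and 54 of 54 at 28 days. All four gaps are positive, so the enumeration leaves out the protected class in Step 1.

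**Step 5: a simple alternative.** Imputing the last day of the month loses 0 of 5,738 PD-first pairs. It errs the other way for pairs in which therapy truly came before PD in the same month: all 5,319 of these (28-day gap) would count as events.

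**The case against.** The strongest reply is that the reach is narrow, and much of that reply stands.

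- **The last dose is a floor.** Part 3 disease samples are scheduled on Day 1, the dosing day (Protocol Appendix A). The PFS event takes the earliest date of a confirmed PD, and treatment after PD is allowed. A patient dosed on or after the day of the first PD sample is fully protected.
- **Confirmation can protect the event.** If PD was first seen in February and seen again on 18 March, and therapy is imputed to 1 March, the February PD is the last assessment before therapy. It counts as confirmed, and the event keeps its date.
- **Frequency is unknown.** Protocol Section 9.5 requires initiation dates for later lines, and Section 12.1 provides checks and queries for missing or inconsistent dates. Nothing shows that partial dates are common, or how often new therapy starts in the month of PD.
- **The early date has a purpose.** It keeps out assessments that might have been made on new therapy.

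The last argument is weaker for PD. Under Protocol Sections 6.3.1 and 9.5, PFS visits stop when subsequent therapy starts. A PD from a scheduled study assessment in the recorded month therefore most likely came first.

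A reader might also infer that the SAP contradicts itself, because note 3 puts PD first. It does not: note 3 begins "If PD or death and the subsequent anti-cancer therapy occur on the same day" and covers only that case. Nor is the day after last dose used whenever the month is missing. With a later year recorded, the rule gives 1 January.

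**Conclusion.** The point holds in a definable case: known year and month, first PD from a study assessment after the last dose, in the recorded month, and after the imputed date. There the SAP's rules give the wrong event status, and nothing in Sections 7.8.1 or 7.8.2.2 prevents it.

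The 93.6% describes possible date pairs within that case and is not a forecast of patients. It should not be read as evidence that median PFS or DOR will be materially too long, because the documents give no count of partial dates.

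It should not be read as a threat to the primary result either. IRC-assessed ORR does not count PD as an event. Assessments after an imputed early therapy date could also be excluded from ORR, but no change to the criterion of at least 33 responders among 118 (SAP Appendix D) is shown. The affected endpoints are secondary, estimated within arm, with no formal comparison between arms (Protocol Section 13.1.3). This is a minor correction worth making because it costs so little.

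**What to change.** Add to SAP Appendix B, for dates with known year and month only:

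*If the earliest date of a PD from a protocol-scheduled study assessment that otherwise meets the SAP confirmation rules lies in the recorded month and after the last dose, impute the later of the current rule and that PD date.*

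The two dates then coincide or PD comes first, and note 3 of Tables 1 and 2 keeps the event.

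Two limits are needed. Do not use a PD recorded as disease status after subsequent therapy. Do not extend the rule to completely missing dates, which have no bounded period and could draw in a PD on later therapy; list those patients instead.

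The cost is one sentence and a small change to the derivation. The downside is that a patient whose new therapy truly began earlier in the same month than the PD would be counted as an event. The end-of-month rule makes the same error. The anchor limits it to PDs from scheduled study assessments and leaves the imputed date unchanged for everyone else.

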Appendix C Algorithms of DLT-like Events

Wording from Protocol Section 8.2	Programmatic algorithm

1) Nonhematologic TEAEs of NCI CTCAE Grade ≥ 3 clearly unrelated to the underlying disease and occurring during the first cycle will be considered DLTs (see Section 10.2 for relatedness guidance), with the following exceptions:
	
For DLT-like events from AE data, check for Grade 3 or higher drug-related nonhematologic TEAEs, i.e. AEs with AETOXGR in (“GRADE 3” “GRADE 4” “GRADE 5”) and AEREL=“RELATED”, then remove the exceptions from 1b to 1e
 
For nonhematologic DLT-like events from laboratory data see instructions in 1a.

a. Asymptomatic laboratory changes (other than renal and hepatic laboratory values, and Grade 4 lipase/amylase) that can be successfully supplemented (reversion of Grade 4 events to Grade ≤ 2, reversion of Grade 3 events to Grade ≤ 1 or baseline) within 72 hours.
	
1) Pull out any Grade 3 or higher renal and hepatic chemistry lab values i.e. where LBTOXGR in (“GRADE 3” “GRADE 4” “GRADE 5”) and LBTESTCD in (“CREAT” “BUN” “BILI” “ALT” “AST”). All Grade 3 or higher results are considered DLT-like events.
 
2) Pull out any Grade 3 or higher chemistry lab values not included in point 1, i.e. where LBTOXGR in (“GRADE 3” “GRADE 4” “GRADE 5”) and LBCAT=“CHEMISTRY” and LBTESTCD not in (“CREAT” “BUN” “BILI” “ALT” “AST”), and keep the records that don’t return to baseline (or go from Grade 3 to 1, or from grade 4 to 2) within 3 days.
 
These results are considered DLT-like events.
 
Note:
 
 • Exclude pre-existing abnormalities, e.g. if a patient has Grade 3 ALT at baseline and post-baseline, this is not considered a DLT-like event since the abnormality was present at baseline. • Renal includes: creatinine, blood urea nitrogen • Hepatic includes: bilirubin, ALT, AST • Lipase and amylase are not collected

b. Grade 3 nausea/vomiting that can be managed subsequently with anti-emetics (Grade 3 nausea or vomiting that persists
	
AEDECOD in (“Nausea” “Vomiting”) and AETOXGR in (“GRADE 3”) and AEDUR ≤ 2

beyond 48 hours with or without appropriate medical intervention will be considered a DLT).
	

c. Grade 3 fatigue lasting less than 72 hours.
	
AEDECOD in (“Fatigue”) and AETOXGR in (“GRADE 3”) and AEDUR <= 3


d. Grade 3 elevation of ALT or AST that resolves to Grade ≤1 or baseline within 7 days.
	
AEDECOD in (“Alanine aminotransferase increased” “Aspartate aminotransferase increased”) and AETOXGR in (“GRADE 3”) and AEDUR <=7 and AEOUT=“RECOVERED/RESOLVED”

e. Grade 3 IRR that responds to symptomatic treatment, without recurrence of Grade 3 symptoms.
	
IRRFL=“Y” and AETOXGR in (“GRADE 3”) Note: IRR events and signs and symptoms are considered for this.

2) The following hematologic TEAEs of Grade ≥3 clearly unrelated to the underlying disease and occurring during the first cycle will be considered DLTs:
	
For DLT-like events from AE data, check for drug-related hematologic TEAEs then search for the following event in 2a. For hematologic DLT-like events from laboratory data see instructions in 2e.

a. Grade ≥3 hemolysis.
	
AEDECOD in (“Hemolysis”) and AETOXGR in (“GRADE 3” “GRADE 4” “GRADE 5”)

b. Grade 4 neutropenia lasting more than 7 consecutive days
	
N/A – see 2e.

c. Grade 4 thrombocytopenia lasting more than 14 consecutive days.
	
N/A – see 2e.

d. Grade 3 thrombocytopenia with clinically significant bleeding.
	
N/A – see 2e.

e. Any other Grade ≥4 hematologic toxicity with the following exception:
 
a. Grade 4 lymphopenia
	
Check for Grade 4 or higher hematology lab values, except lymphocytes per the exclusion note i.e. LBTOXGR in (“GRADE 4” “GRADE 5”) and LBCAT=“HEMATOLOGY” and LBTESTCD not in (“LYM”). Apply the following to the remaining parameters:
 
 1) For all parameters except platelets and neutrophils i.e. LBTESTCD not in (“NEUT” “PLAT”), any occurrence of a Grade 4 or higher result will be considered a DLT-like event. 2) For platelets and neutrophils, i.e. where LB.LBTESTCD in (“NEUT” “PLAT”),

	
keep the record if the patient's result doesn't return to the following prior to or including the next scheduled dose date (use exposure dates for this):
 
Platelets $\geq 50 \text{ } 10^9/\text{L}$ Neutrophils $\geq 1 \text{ } 10^9/\text{L}$
 
Scheduled dose date = date the next dose should have occurred, e.g. schedule D would be 28 days after the previous dose.

3) An incomplete recovery from treatment-related toxicity causing a >2 -week delay in the next scheduled infusion before the initiation of Cycle 2 (or next cycle if after cycle 1) will be considered a DLT.	Any TEAEs with AEREL="RELATED" and AEACN="DOSE DELAYED" and the next dose was delayed for >14 days

Assumptions:

- 1) Hematologic AEs include the following PTs:

Hematology collection from protocol	Preferred term
Hematocrit	“Anaemia” “Hemolysis”
Hemoglobin	“Anaemia” “Hemolysis”
Leukocytes with differential	“Leukopenia” “White blood cell count decreased”
Neutrophils (ANC)	“Neutropenia” “Neutrophil count decreased” “Febrile neutropenia”
Platelet (count)	“Thrombocytopenia” “Platelet count decreased”
Lymphocytes	“Lymphopenia” “Lymphocyte count decreased”

Note: PTs may change with coding updates.

- 2) Only include TEAEs which are related to study drug.
- 3) Duration is calculated in days, not hours e.g. 48 hours = 2 days (This would check the day of AE and the next day).
- 4) For 'Clinically significant bleeding', this is included in the non-hematologic AE part. Considering 'clinically significant' as Grade 3 or higher. No need to check for the thrombocytopenia, that is checked via the laboratory data.

